10. HUMAN SUBJECTS PROTECTIONS

This protocol and the informed consent document (Appendix A) and any subsequent modifications will be reviewed and approved by the Steering Committee, IRB, and DSMB responsible for oversight of the study. A signed consent form will be obtained from the subjects.

The total sample size for the primary outcome for this study will be approximately 1262 patients who have consented to participate. The original sample size approximated 100 patients at each clinical site, although some sites will enroll up to 140 consented participants due to limited enrollment by other sites resulting from institutional COVID pandemic issues..

- Participating patients at a clinical site randomized to CSC/PSC arm will be followed by the Coordinator to collect the same acute in-hospital metrics to measure care quality, health status, and outcomes and will also be contacted via telephone by the blinded personnel at the UAB SDCC SRU to assess primary outcomes.
- The patient and their caregiver (or their legally authorized representative, if patients are unable to provide consent) will be approached to participate in the study ideally during hospitalization or within 5 business days of hospital discharge ideally (to a maximum of 14 total days) to allow for data collection of specific acute in-hospital metrics). Caregivers may be consented at any time during the C3FIT study, but no data will be collected until consent is obtained. At research visits, the following will be obtained: (1) demographic and other data collection; (2) follow-up data collection specific to the CSC/PSC arm; and (3) contact via telephone survey to collect SIS and smRS outcome data.
- C3FIT's population will include patients with all stroke subtypes and levels of severity, regardless of gender, race, ethnicity, or socioeconomic status. Each Site will recruit from their geographically eligible patients (who have a discharge diagnosis of stroke according to their ICD-10 code) until approximately 100 patients are consented, although some sites will enroll up to 140 consented participants due to limited enrollment by other sites due to institutional COVID PANDEMIC issue.

B. Adequacy of Protection Against Risks

Recruitment and Informed Consent. The acute in-hospital study sample will include patients admitted to the hospital with suspected stroke symptoms. Potential participants (both patient and caregiver if available) will be approached for recruitment ideally within 5 business days post discharge ideally (to a maximum of 14 total days) for the participant. In the event that the patient is unable to provide consent, their surrogate can be consented. Patients will be identified by study personnel from ED and stroke service admission logs; pilot data suggests nearly complete case ascertainment. To assure that acute in-hospital recruitment and informed consent procedures are followed consistently across Sites, a guidance document will be prepared in consultation with Site PI's and other patient, caregiver and organizational stakeholders, and Site personnel will be trained consistently by CCC staff.

The post-hospital discharge study sample will include patients and caregivers who have a discharge diagnosis of stroke and who reside in each clinical site's defined geographic area. Potential participants will be approached prior to hospital discharge regarding their interest in

participating in the study, and every effort will be made to consent both patient and caregiver at that time.

Patients and caregivers at a CSC/PSC site will be managed according to a traditional post-acute JC-certified CSC/PSC design, including a phlebotomy (draw blood) for cholesterol and HBA1C according to the study time schedule in Figure 7.

The consent process will begin at hospital admission at a C3FIT clinical site. The PI at the site or his/her Co-I designee will provide information to the patient and/or caregiver about the nature of the trial, the two arm comparator groups and the randomization of the site. The fact that the C3FIT study does not involve an investigational drug or device will be discussed with the patient and caregiver. Potential participants will be made aware of the scientific basis for the comparison of methods of care delivery, and the clinical equipoise of the investigators. Information on the requirements of the participants will be discussed: (1) to allow appropriate outcome scales to be obtained, (2) the approximate time involved in obtaining these scales based on or pilot experience, (3) that some of the outcome scales will be obtained by phone by blinded interviewers at the UAB SDCC SRU, (4) and that common laboratory tests will be obtained that would be appropriate for monitoring any person who suffered a stroke.

Potential and enrolled participants will: (1) be assured that they may withdraw consent at any time and do not have to provide a reason for their withdrawal; (2) have the right to speak with a member of our patient/stakeholder advisory group if they so choose to obtain additional information; and (3) be provided access to study personnel at their C3FIT clinical site (including the PI) to answer any questions or address concerns. In addition, the C3FIT personnel at the CCC are available for any questions or issues they identify. Potential participants will be assured that study personnel will be well trained, are familiar with guidelines for human subject's protection, and will have completed appropriate human subject's protection training as required by their site and the C3FIT Central IRB. A member of the Stakeholder Committee for C3FIT is a medical ethicist who has assisted in the design of the pilot study and, as such, will be available as a resource to C3FIT study personnel if specific ethical issues arise.

B. Potential Risks to Subjects and Protections

Potential risks for C3FIT participants and proposed methods to reduce these risks are described below. A member of the Stakeholder Committee for C3FIT is a medical ethicist who has assisted in the design of the pilot study and, as such, will be available as a resource to C3FIT study personnel if specific ethical issues arise.

- 5) *Breach of confidentiality of medical information in the acute in-hospital or outpatient setting – minimal risk.* All data will be stored in encrypted, password-protected databases that meet mandated IT security standards and will include subject identifiers (name, address, date of birth, and medical record numbers) necessary to maintain contact during the study.
- 6) *Anxiety/discomfort – minimal risk.* Participants will be assured that all study-related data and information (including both outcome assessment and monitoring data) will be kept confidential by the PI and study personnel, any questions and concerns can be addressed at any time, and participants can refuse to answer any question or not participate at any time during the study.

- 7) *Harm from physical and clinical assessments or measurements conducted as part of the outpatient CSC/PSC program – minimal risk.* Physical assessments like the NIHSS (measured prior to hospital discharge), the SIS, and smRS are standard assessment scales utilized in clinical practice. C3FIT study personnel will undergo training and certification in these scales, which have no recognized physical harm. Other scales used, including the primary outcome scale (SIS), have been used in many clinical situations/studies with no recognized harm.
- 8) *Discomfort and/or harm from blood draws to assess cholesterol level and HbgA1c – minimal risk.* Standard phlebotomy techniques will be used as in typical care. The minimal pain and risk of fainting will be acknowledged to potential participants, and participants may decline some or all of the blood draws.

Since no investigational device is involved in the C3FIT study, we anticipate few adverse events. However, our conservative approach is to provide several layers of protection for our study participants: (1) the informed consent process itself; (2) access to the C3FIT personnel, including the C3FIT nurses and physician Site PI; (3) access to the CCC staff, including the C3FIT PI; (4) a Central IRB at Vanderbilt to provide consistency across 18 C3FIT Sites; and (5) a Data and Safety Monitoring Board (DSMB) that will review patient outcome data; and (6) human subjects research protections using the CITI certification as required by the Central IRB.

Adverse events (physical, behavioral, or psychological) will be reported to the Clinical Site PI or the SDCC; they will report these adverse events per guidelines in a timely fashion to the CCC, where they will be reviewed by the PI, Project Manager and forwarded to the DSMB.

C. Potential Benefits of the Proposed Research

Benefits for Patients. The major benefit to patients will accrue to future patients who benefit from the information gained from this study to design a patient-centered stroke healthcare delivery system that is comprehensive, integrated, and caregiver/family-focused. Many of the current issues faced by stroke patients involve lack of defect free stroke care in the in-hospital phase of care, leading to longer lengths of stay and in-hospital complications. These complications can lead to loss of QOL over many years. Lack of defect free care also plagues the post-hospital phase of care where stroke recurrence leads to readmissions and less Time at Home. Patients can also benefit by access to results of C3FIT to inform their choices in health care based on data that identifies the most effective and efficient care.

Based on positive results of C3FIT, patients could also benefit by having the potential for home care management, avoiding time and travel costs for outpatient clinic visits. Patients will have screening for HbgA1C and cholesterol to measure risk factor control at-target which may help identify targets of therapy. Patients could also benefit by having their caregivers supported by study personnel reducing caregiver strain. Because patients are involved in the design, implementation and dissemination of C3FIT outcomes that matter to them will be foremost in the study design.

Benefits for Caregivers. The major benefit to caregivers will accrue to future caregivers where the information gained from this study can be used to design a patient-centered stroke healthcare delivery system that is comprehensive, integrated, and caregiver/family-focused. Such a system may encourage recovery in their associated patient and limit stroke recurrences and readmissions.

If results from C3FIT are positive, caregivers could have the potential advantage of home visits, avoiding the stress, time commitment, and travel costs of clinic visits. Caregivers could potentially benefit by having a team that monitors their stress level and offers support.

Benefits for Organizational Stakeholders and Society. Organizational stakeholders will benefit by having access to high quality data to inform decisions regarding design and implementation of the most efficient and effective stroke delivery system.

D. Risk-to-Benefit Ratio

C3FIT risks to participants are reasonable. C3FIT does not involve any investigational drug or device, so the risks of unknown or unrecognized side effects of investigational drugs and devices are not an issue. C3FIT involves several blood specimen collections (HbA1C and cholesterol) with associated pain from the needle stick. This discomfort is transient and considered minimal. These tests would be considered standard of care in a stroke patient. The collections themselves are to obtain lab values that will be used to document control at target of risk factors and inform decisions about best medication or other therapy based on nationally accepted guidelines. Testing procedures involve only grading scales often used in practice (i.e., NIH Stroke Scale, Simplified Modified Rankin Scale (smRS), or scales that are commonly used in stroke clinical trials for outcome). The information requested will include some information about sexual, urinary, and bowel function but will be obtained by trained medical personnel with a minimum of patient distress. The time involved in obtaining information from patients and caregivers is carefully considered. Only those scales determined critical to patient management and documentation of key functional and QOL outcomes are utilized. The timing of administration of these scales is also carefully chosen to not provide undue time commitment or stress at any visit. Given the minimal risks and significant potential benefits the risk benefit ratio seems reasonable and quite acceptable.

Importance of the Knowledge to be Gained. We have discussed the opportunity to improve stroke care delivery given the lack of defect free care, complications, recurrences, and lack of risk factor control documented for stroke patients. In addition, the opportunity to focus on stroke outcomes that are patient-centered will significantly improve patient and caregiver engagement in their intervention and recovery journey resulting from stroke. Organizational stakeholders such as the JC and the ASA, who are tasked with offering improvement programs that are informed by high quality scientific evidence, will find data from C3FIT invaluable, as Level 1 evidence to assist in identifying the appropriate focus for resources and effort does not currently exist. Vascular neurologists (VNs) and rehabilitation and internal medicine physicians will find that the results of this trial will help design care delivery approaches that provide the most appropriate patient centered functional and QOL outcomes rather than depending on compliance with process measures that may not contribute to these more important outcomes.

As in any research effort, much of the time, stress, and risk of the project is born by participants. It is hoped that including them as Research Partners may help to ally some of this burden. In any event, they are to be honored for their involvement.

Data and Safety Monitoring Plan. A formal Data and Safety Monitoring Board (DSMB) will be convened at regular intervals (for example, twice a year) to review and monitor recruitment, data security, and patient safety. The DSMB and development of the formal DSMB Plan is described in Section 8.

ClinicalTrials.gov. This randomized trial has been registered, and results will be reported in ClinicalTrials.gov as encouraged by NIH and required by Public Law 110-85.

E. Inclusion of Women and Minorities

This study has no exclusion criteria based on gender, race, or ethnicity. We anticipate that patients recruited to our study will reflect the demographic profile of the general stroke population, which proportionally includes more older adults than younger and good representation of minorities. While the age-adjusted incidence of stroke (primarily ischemic stroke) in men is approximately 30% higher than in women, more women have strokes because women live longer than men. However, because they are older at time of stroke, women have more co-morbidities so they may be less likely to meet some of inclusion/criteria.

F. Subject Confidentiality

All laboratory specimens, evaluation forms, reports, video recordings, and other records that leave the site will be identified only by the Study Identification Number (SID) to maintain subject confidentiality. All records will be kept in a locked file cabinet. All computer entry and networking programs will be done using SIDs only. Clinical information will not be released without written permission of the subject, except as necessary for monitoring by IRB, PCORI, or the DSMB.

G. Study Modification/Discontinuation

The study may be modified or discontinued at any time by the IRB, PCORI, or the DSMB as part of their duties to ensure that research subjects are protected.

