Study Design. C3FIT is a multicenter, randomized, single blinded, Phase III, cluster randomized trial. Sites will be stratified by patient admission volume and geographic location; subsequently, each site will be randomized to one of two patient care management strategies: the CSC/PSC versus ISPU model.

Outcomes. C3FIT’s primary outcomes are the SIS and smRS at 12 months.

Sample Size and Population. Based on the primary outcome, the study was originally designed for a total sample size of approximately 1800 patients, with approximately 18 sites. However, due to the challenges of the COVID-19 pandemic the sample size was decreased to 1,262 and the number of sites were increased to 22. The Statistical and Data Coordinating Center (SDCC) at the University of Alabama determined the change in sample size would not influence the study statistical measures and/or study power, and our funder, PCORI, approved of the changes.

Interventions. Coordinated care (including in-home/in-patient rehabilitation and skilled nursing or extended care facility visits) will be provided based on protocol-based coordination of post-acute in-home/facility care for ISPU Site patients, while CSC/PSC patients will be managed per standard CSC/PSC protocol with no additional study related management post discharge. Clinical site personnel will be provided with training specific to the arm to which they are randomized.

Duration. Patients will be followed at the site level for one year after enrollment.

1. **STUDY OBJECTIVES**

The current standard of stroke care is the JC-certified CSC/PSC care system, a collection of proven individual processes of care, but a system that lacks coordination for the post-stroke care of patients. The C3FIT trial serves as the opportunity to assess potential impact on patient QOL and functional outcomes resulting from the improved integration of care provided by the ISPU approach.

C3FIT's overall goal is to assess if patient outcomes are improved when the CSC/PSC system is supplemented with an Integrated Stroke Practice Unit (ISPU) system of care, a patient-centric model of care involving the patient and caregiver/family that coordinates care from the acute management through the rehabilitation and recovery of the patient.

A. Hypotheses

C3FIT's *Primary Hypothesis* is that the ISPU model of care will show improved mean level SIS and smRS scores at 12 months compared to the CSC/PSC model of care.

The *Secondary Hypotheses* are:

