6. BASELINE AND FOLLOW-UP ASSESSMENTS AND LABORATORY EVALUATIONS

The following outlines the Data Paradigms for Stroke Mobile based on obtained values for various scales and data points utilized. The guidelines establishing blood pressure and cholesterol goals are from the American Heart and Stroke Association.⁸

A. On-Study/On-Intervention Evaluations

The schedule of evaluations occurring after randomization while the subject is on-study and on (or about to start) intervention along with allowable time window in which evaluations may take place (± 30 days with a target of ± 14 days) is shown in Tables 7 and 8. Primary and secondary outcomes are considered a mandatory part of the protocol; remaining measures will be collected if patient/caregiver are able and/or available.

Table 7. Data Collection Paradigm: ISPU Arm, Stroke Central and Stroke Mobile

Item/Metric	In Hospital Prior to Discharge	Post Discharge Visit											
		Day 0-14	Month of Visit to Home/Facility										
		1	2	3	4	5	6	7	8	9	10	11	12
Informed Consent Confirmed	X	X	X	X	X	X	X	X	X	X	X	X	X
Demographics (Age, Gender, Race/Ethnicity, Marital Status, Zip Code of Residence, Income, and Education)*	X			X			X						X
Caregiver/Family identified*	X			X			X						X
Medical Record Number (MR #)*	X												
Get-With-The-Guidelines (GWTG) in-hospital data*	X												
Patient Medical History	X			X			X						X
Complications* ¹	X			X			X						X
National Institutes of Health Stroke Scale (NIHSS)*	X	X	X	X	X	X	X	X	X	X	X	X	X
Stroke Subtype*	X												
Prior stroke/Transient Ischemic Attack (TIA)*	X												
Risk factor profile* ²	X												X
Cholesterol panel or LDL*	X			X			X						X
Hemoglobin A1C (HBA1C)*	X			X			X						X
Perceived Support				SRU			SRU						SRU
Stroke Impact Scale (SIS)				SRU			SRU						SRU
Simplified Modified Rankin Scale (smRS)	X			SRU			SRU						SRU
Blood Pressure (BP) Control: at target	X	X	X	X	X	X	X	X	X	X	X	X	X
Lipid Control: LDL, at target	X			X			X						X
Diabetes Control: HBA1C, at target	X			X			X						X
Smoking Status	X	X	X	X	X	X	X	X	X	X	X	X	X
Body Mass Index (BMI)	X	X	X	X	X	X	X	X	X	X	X	X	X
Diet Assessment	X	X	X	X	X	X	X	X	X	X	X	X	X
Exercise Assessment	X	X	X	X	X	X	X	X	X	X	X	X	X
Mortality surveillance		X	X	X	X	X	X	X	X	X	X	X	X
Recurrence surveillance		X	X	X	X	X	X	X	X	X	X	X	X
Readmission surveillance		X	X	X	X	X	X	X	X	X	X	X	X
Time at Home		X		SRU			SRU						SRU
Depression History	X												
Depression: Patient Health Questionnaire (PHQ-9)		X	X	X	X	X	X	X	X	X	X	X	X

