10. HUMAN SUBJECTS PROTECTIONS

This protocol and the informed consent document (Appendix A) and any subsequent modifications will be reviewed and approved by the Steering Committee, IRB, and DSMB responsible for oversight of the study. A signed consent form will be obtained from the subjects.

The total sample size for the primary outcome for this study will be approximately 1800 patients (approximately 100 patients at each clinical site, although some sites will enroll up to 140 consented participants due to limited enrollment by other sites due to institutional COVID PANDEMIC issues) who have consented to participate.

- Participating patients at a clinical site randomized to ISPU arm will be followed by Stroke Central to collect the same acute in-hospital metrics to measure care quality, health status, and outcomes and will also be contacted via telephone by the blinded personnel at the UAB SDCC SRU to assess primary outcomes. However, ISPU patients will also be assessed monthly by Stroke Mobile for 1-year in their home to collect specific metrics that will evaluate the patient and caregiver/family for potential issues and provide follow-up care and targeted education and support.
- The patient and their caregiver (or their legally authorized representative, if patients are unable to provide consent) will be approached to participate in the study ideally during hospitalization or within 5 business days of hospital discharge ideally (to a

maximum of 14 total days) to allow for data collection of specific acute in-hospital metrics. Caregivers may be consented at any time during the C3FIT study, but no data will be collected until consent is obtained. At research visits, the following will be obtained: (1) demographic and other data collection; (2) follow-up data collection specific to the ISPU arm; and (3) contact via telephone survey to collect SIS and smRS outcome data.

- C3FIT's population will include patients with all stroke subtypes and levels of severity, regardless of gender, race, ethnicity, or socioeconomic status. Each Site will recruit from their geographically eligible patients (who have a discharge diagnosis of stroke according to their ICD-10 code) until approximately 100 patients are consented, although some sites will enroll up to 140 consented participants due to limited enrollment by other sites due to institutional COVID PANDEMIC issues.

A. Adequacy of Protection Against Risks

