4. STUDY DESIGN

C3FIT is a randomized comparative effectiveness trial (CET) of two care delivery methodologies at approximately 18 clinical sites. Primary and secondary outcomes are described in Section 1.

A. Disease-specific Enrollment Criteria

Clinical Indicators. Definitive stroke will be defined by ICD-10 code criteria. Definitions will be based on ICD-10 criteria (see Table 4). Investigators will use tests and assessments deemed appropriate for an individual patient to determine the appropriate diagnosis. Additional stroke subtype categorization will occur using the TOAST Criteria as performed by C3FIT clinical site investigators.

Prior Therapy. There is no exclusion for prior therapy.

Demographic Characteristics. The clinical sites have been carefully selected with the goal of providing nationwide representation, urban and rural representation, inclusion of both men/women and all race/ethnic groups affected by. Patients aged 18 and older are eligible with no upper age exclusion criterion.

Contraindications. Since no drugs or experimental devices are utilized in this trial there are no specific contraindications.

Pregnancy Exclusions. There is no exclusion for pregnancy or planned lactation and no inherent risk from the proposed intervention.

B. Randomization

C3FIT is randomized at the facility (clinical site) level rather than the individual patient level. Randomization at the facility level is appropriate, as the proposed comparator arms could not be reasonably instituted at the patient level for a system change design. Clinical sites were stratified by geography, balanced by patient volume, and randomized to the CSC/PSC or ISPU model.

C. Site Selection

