6. BASELINE AND FOLLOW-UP ASSESSMENTS AND LABORATORY EVALUATIONS

The following outlines the Data Paradigms for the CSC/PSC arm based on obtained values for various scales and data points utilized. The guidelines establishing blood pressure and cholesterol goals are from the American Heart and Stroke Association.⁸

A. On-Study/On-Intervention Evaluations

The schedule of evaluations occurring after randomization while the subject is on-study and on (or about to start) intervention along with allowable time window in which evaluations may take place (± 30 days with a target of ± 14 days) is shown in Table 7. Primary and secondary outcomes are considered a mandatory part of the protocol; remaining measures will be collected if patient/caregiver are able and/or available.

Table 7. Data Collection Paradigm: CSC/PSC Arm

Item/Metric	In Hospital Prior to Discharge	Post Discharge Visit												
		Day 0-14	Month of Visit to Home/Facility											
			1	2	3	4	5	6	7	8	9	10	11	12
Informed Consent Confirmed	X			X			X						X	
Demographics (Age, Gender, Race/Ethnicity, Marital Status, Zip Code of Residence, Income, and Education)*	X			X			X						X	
Caregiver/Family identified*	X			X			X						X	
Medical Record Number (MR #)*	X													
Get-With-The-Guidelines (GWTG) in-hospital data*	X													
Complications* ¹	X			X			X						X	
Patient Medical History	X			X			X						X	
National Institutes of Health Stroke Scale (NIHSS)*	X												X	
Stroke Subtype*	X													
Prior stroke/Transient Ischemic Attack (TIA)*	X													
Risk factor profile* ²	X												X	
Cholesterol panel or LDL*	X			X			X						X	
Hemoglobin A1C (HBA1C)*	X			X			X						X	
Perceived Support				SRU			SRU						SRU	

Stroke Impact Scale (SIS)				SRU			SRU						SRU
Simplified Modified Rankin Scale (smRS)	X			SRU			SRU						SRU
Blood Pressure (BP) Control: at target	X			X			X						X
Lipid Control: LDL, at target	X			X			X						X
Diabetes Control: HBA1C, at target	X			X			X						X
Smoking Status	X			X			X						X
Body Mass Index (BMI)	X			X			X						X
Diet Assessment	X			SRU			SRU						SRU
Exercise Assessment	X			SRU			SRU						SRU
Mortality surveillance				X			X						X
Recurrence surveillance				X			X						X
Readmission surveillance				X			X						X
Time at Home				X			X						X
Depression: Patient Health Questionnaire (PHQ-9)				X			X						X
Caregiver Strain Index (CSI)				X			X						X

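### The telephone interviewers who assess smRS and SIS are called blinded, but the two Tables 7 give them different items by arm, against Table 1, and no safeguard for their blind is described

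*Protocol*

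**What the plan says.** The Summary of each protocol states the design: "C3FIT is a multicenter, randomized, single blinded, Phase III, cluster randomized trial". The only masking then described is that of the SRU staff at the coordinating center. Section 10 of the CSC/PSC protocol says that patients "will also be contacted via telephone by the blinded personnel at the UAB SDCC SRU to assess primary outcomes", and section 10 of the ISPU protocol says the same of its own patients ("contacted via telephone by the blinded personnel at the UAB SDCC SRU to assess primary outcomes").

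Section 6 of each protocol refers to its own Table 7 for what is assessed and when (the ISPU protocol adds Table 8). In both, the "Perceived Support", SIS and smRS rows are SRU cells at 3, 6 and 12 months. The other SRU cells differ. In the ISPU Table 7, time at home goes to the SRU ("Time at Home X SRU SRU"), while diet and exercise carry a plain X. In the CSC/PSC Table 7, the "Diet Assessment" row and the exercise row go to the SRU, while time at home carries a plain X.

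Table 1, printed in both protocols, marks SIS, smRS, diet, exercise and time at home with the same plus sign at 3, 6 and 12 months. The plus sign appears to be the one explained by the SRU-only footnote.

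On allocation, section 4.B says "C3FIT is randomized at the facility (clinical site) level rather than the individual patient level". Section 10.A has the consent discussion cover the two arms and the randomization of the site. Section 10 of the ISPU protocol adds that "ISPU patients will also be assessed monthly by Stroke Mobile for 1-year in their home".

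**The concern.** Patients and treating teams cannot be assumed masked in this trial, so the interviewer's blind is the only protection described against assessor expectation. It could fail in two ways.

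- **Item list.** If the SRU works from Table 7, a call that asks about time at home belongs to one arm, and a call that asks about diet and exercise belongs to the other.
- **Disclosure.** An ISPU patient may mention the home team. Because a site has only one arm, an interviewer who can tell which site a patient comes from would then know the arm of that site's later patients.

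Neither protocol nor the SAP describes a common script, a fixed item order, concealment of site from the interviewer, a request that participants not describe their care, or a record of unmasking.

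The outcome most exposed is smRS, which the interviewer assesses. SAP section 3.2 (where the scale is called mRS) splits it at 0–2 versus 3–6, so a small shift in probing or scoring near the cut can move a patient from one category to the other. SIS is less affected by interviewer masking, because it is reported by patients who are themselves unblinded.

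**Working it through.** **Step 1. SRU items at 3, 6 and 12 months, side by side.**

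| Item | Table 1 (both protocols) | ISPU Table 7 | CSC/PSC Table 7 |
|---|---|---|---|
| SIS | SRU | SRU | SRU |
| smRS | SRU | SRU | SRU |
| Perceived support | not listed | SRU | SRU |
| Diet | SRU | plain X, every visit | SRU |
| Exercise | SRU | plain X, every visit | SRU |
| Time at home | SRU | SRU | plain X |

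The Table 1 column reads the plus sign as the SRU-only marker. Three items are common to both Tables 7. One is SRU only in ISPU (time at home), and two are SRU only in CSC/PSC (diet and exercise). Against Table 1, the ISPU Table 7 lacks diet and exercise as SRU items, and the CSC/PSC Table 7 lacks time at home. Table 1 implies one common call; the two Tables 7 imply two different calls. They cannot both be the operating instruction.

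**Step 2. How many patients share an arm within a site.** The reduced sample size is 1,262. The number of sites is 22 in the ISPU Summary, 23 in the CSC/PSC Summary, and 21 with data in SAP section 1.

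- 1,262/21 = 60
- 1,262/22 = 57
- 1,262/23 = 55

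The average is therefore 55 to 60 patients per site, and section 9.A allows up to 140 at some sites.

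**Step 3. Illustration of disclosure (assumed inputs).** With 60 patients and three calls each, an ISPU site generates about 180 calls if all are completed. Assume five interviewers share them equally (180/5 = 36 calls each), calls are independent, the interviewer can link patients to the site, and a proportion p of calls mentions the home visits. The documents give none of these inputs.

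- Chance that a given interviewer hears at least one disclosure from the site: 1 − (1 − p)^36
- Average share of that interviewer's calls made after an earlier disclosure: 1 − [1 − (1 − p)^36]/(36p)

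| p (assumed) | At least one disclosure | Share of calls made after one |
|---|---|---|
| 1% | 30% | 16% |
| 2% | 52% | 28% |
| 5% | 84% | 53% |

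The second column is the relevant one for bias, because a disclosure on the last call affects no later score. Even rare remarks could unmask a material share of calls, but only if the patient-to-site link exists.

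**Step 4. Effect on the primary outcomes.** No figure can be derived. The documents give neither the rate of unmasking nor the effect of unmasking on smRS or SIS scores.

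**The case against.** The best answer is that Table 1, identical in both protocols, already describes one common SRU set. The plain X for diet and exercise in the ISPU Table 7 runs through every monthly visit, so it may record Stroke Mobile monitoring in addition to an SRU call. That is possible, but nothing says so, it does not explain the time-at-home row in the CSC/PSC Table 7, and section 6 points to Table 7 as the defining schedule. The contradiction stands.

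Several stronger readings are tempting and are not supported:

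- **That the call sheet reveals the arm.** No call sheet or script is in the documents. Questions on diet, exercise or time at home do not name an arm; the interviewer would have to know or learn which list goes with which arm.
- **That perceived support is asked before SIS and smRS and so prompts disclosure.** Row order in a schedule table is not call order.
- **That one remark unmasks a whole site.** This needs a patient-to-site link that the documents do not state. Section 10.F says that records leaving the site carry only the study ID and that computer entry uses only that ID, which bears on the link. It is a confidentiality rule, though, and does not say what an SRU caller sees; section 10.B also says identifiers are kept so that contact can be maintained.
- **That an ISPU site is almost certain to be unmasked.** Over 180 calls, 1 − (1 − p)^180 gives 84%, 97% and above 99.9% for assumed p of 1%, 2% and 5%. This is the chance of at least one disclosure at any time, not the share of outcomes scored unmasked.
- **That a positive result could not be separated from assessor expectation.** Suppose awareness moved 2–5% of patients across the smRS cut. The spurious difference would be 2–5 points, against a standard error for a crude 12-month difference of √[2 × 0.25 × (1 + 59.1 × 0.05)/631] = 5.6 points (50% good outcome and ICC 0.05 assumed), or 0.4–0.9 standard errors. The shift itself has no source in the documents, and applying it in full treats nearly all patients as affected.

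**Conclusion.** The point holds as a contradiction with a consequence for masking. The two Tables 7 assign different SRU items by arm, Table 1 assigns the same items in both, and following Table 7 as written means arm-specific calls for an interviewer-assessed primary outcome. No safeguard for the interviewer's blind is described. The documents do not show that the blind was broken; they show that it is not protected as written.

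What is firm is the difference of one item against two in the SRU lists, and an average of 55 to 60 patients per site sharing one arm. What is conditional is that the SRU follows Table 7, that interviewers know or learn the pattern, and, for spread within a site, that they can link patients to sites. The consequence is most serious for smRS and weaker for SIS. This should be corrected because the remedy is cheap, not because a large bias has been demonstrated.

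**What to change.** - Reconcile Table 1 with both Tables 7 so that one identical SRU script serves both arms.
- Have smRS and SIS completed and locked before any other item is opened, with time at home and perceived support last.
- Withhold site and arm from the interviewers, including any site-coded part of the study ID.
- Open each call by asking the participant not to describe the care team or visits.
- Add one field recording whether the arm became apparent before smRS was completed.
- In the SAP, report unmasking by arm. Treat any analysis that excludes unmasked calls as supportive only: those calls will come mostly from ISPU patients who mention home visits, so excluding them conditions on a post-randomization event and can itself bias the comparison.
- SAP section 3.3 refers to recruitment in the past tense, so some calls may already have been made. For those, state which table was followed and report the SRU items collected by arm.

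The cost is a slightly longer call, one extra data field and a short addition to the SAP. No extra staff or visits are needed.
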